	5.5	CONSENT	1/				
6	ADV	ERSE EVENTS					
	6.1	Definitions					
	6.2	REPORTING PROCEDURES					
	6.3 6 4	NON SERIOUS AES					
	0.4	SERIOUS AES	10				
7	ASSE	ESSMENT AND FOLLOW-UP					
8	STAT	FISTICS AND DATA ANALYSIS					
9	REG	ULATORY ISSUES	20				
	9.1	ETHICS APPROVAL	20				
	9.2	CONSENT					
	9.3						
	9.4 05		21 21				
	9.5	Funding	21 21				
	9.7	Audits					
10	STU	DY MANAGEMENT					
11							
17							
12							
	REFERENCES						

Glossary of Terms

CSP: Conduction system pacing CT: Computed tomography ECG: Electrocardiogram EGM: Electrogram HBP: His-bundle pacing ICE: Intracardiac echocardiogram LBBB: Left bundle branch block LBP: Left bundle pacing LBAP: Left bundle area pacing LV: Left ventricle LVAT: Left ventricular activation time MRI: Magnetic resonance imaging RV: Right ventricle TOE: Transoesophageal echocardiogram TTE: Transthoracic echocardiogram

Study Summary

TITLE	Solutions to the challenges of conduction system pacing				
DESIGN	Cohort observational study and interventional at validation phase				
AIMS	 Provide a simplified standardised conduction system lead implantation protocol Define capture diagnostics of left bundle pacing from left septal pacing 				
OUTCOME MEASURES	 Primary Outcomes: A1: Success rates of conduction system lead implant (novel workflow vs conventional methods) B1: Assess accuracy of conduction system diagnosis by the device with additional information from 2-lead ECG Secondary Outcomes: A2: Procedure and fluoroscopy times of the streamlined workflow to current conventional methods of His-bundle and Left-bundle pacing A2: Procedure and fluoroscopy times of the streamlined workflow of conduction system implant to current right ventricular pacing A2: Assess capture threshold of His-bundle and Left-bundle pacing from the optimised workflow to that of conventional methods of conduction system implantation A2: Define left bundle area capture diagnostics and delineate differences between left ventricular septal pacing. B2: Improvement in device battery life with novel device algorithm applied 				

POPULATION	Patients with any indication for a pacemaker
ELIGIBILITY	 Inclusion criteria: Indication for pacemaker implant Exclusion criteria: Unable to give consent Children age < 18 years or adults >100 years old
DURATION	3 years

1. Introduction

1.1 Background

Discovering how to clinically deliver conduction system pacing efficiently could be a paradigm shift. Early work on conduction system pacing focused on the His bundle, with right atrial mapping for the His signal and deployment of a lumenless pacing lead(1). Left bundle pacing (LBP) then emerged as an alternative, approaching via the basal right ventricular septum to deploy a lead through the septum to capture the left bundle on the left side of the septum(2,3)

Current literature report improved left ventricular function, heart failure outcomes and mortality in conduction system pacing(4,5). Additionally, LBP has a larger target area, can be done with low capture thresholds, has better threshold stability and large amplitude R waves(3). Widespread roll out of conduction system pacing clinically, however, faces three major challenges.

Challenge A1: Identifying target area for lead deployment

Despite growing adoption, conduction system pacing implants remains challenging. Even experienced device consultants take time to learn the technique. Experienced centres achieve implant success of 95%, but centres with new conduction system implanters (but highly experienced pacemaker implanters) have rates as low as 56%(6,7).

Fluoroscopic interpretation is challenging, for several reasons. The target area is smaller than conventional right ventricular pacing, and can be even smaller when there is fibrosis in the septum. The chambers may well be dilated, which displaces not only the fluoroscopic position of the target, but also its orientation. The lead can also be difficult to advance, because of septal fibrosis, unrecognised lead entanglement and unclear trans-septal trajectory. Interpretation of surface ECG and lead data is not straightforward either: there are many levels in the conduction system at which block can occur and it is difficult to distinguish them confidently. Lead entanglement and mal-orientation may be detectable with elaborate equipment such as intracardiac echocardiography (ICE) but we do not know what fluoroscopic or electrical features might provide routine clinical operators with a timely warning. Previous approaches to address these issues have involved normal-heart cadaveric studies which do not give the electrical context of a clinical implant(8).

Challenge A2: Defining left bundle area capture.

Although there are various expert consensus' in the diagnosis of left bundle capture, the capture diagnostics has yet to be validated. In view of the limitations of left bundle capture confirmation, it remains difficult to establish confidently if there is left conduction system capture rather than left ventricular septal capture only. Furthermore, it is unclear if there is a clinically relevant advantage to left conduction system capture to left ventricular septum capture. This requires further investigation.

The paced activation patterns of the left ventricle during the lead deployment will be collected; at the left ventricular septal area (defined as more than half way beyond the septum) and the left bundle. At these points the electrical data from the pacing lead will be collected. The distal and proximal left bundle will be paced and restoration of physiological left ventricular activation will be assessed.

Challenge B: Reduced battery longevity due to high thresholds as result of limited conduction system capture discrimination by the device.

In conventional pacing, it is easy to describe to the device how to detect adequate capture, and therefore easy to have the device monitor adequacy of capture and adjust output to strike an efficient balance between ensuring capture and minimising energy consumption(9) (**Figure 1**). In conduction system pacing, we do not know how to check conduction system capture reliably using purely device-based information. Therefore, we cannot safely set the output to optimise battery life; instead, outputs are set unnecessarily high to ensure continued conduction system capture.

Checking correct capture is more difficult for conduction system pacing than conventional. It is not enough to detect capture: the device must confidently distinguish between several possible response patterns. Each patient may exhibit several patterns at different outputs. Misinterpreting the type of capture can cause harm. For example, in heart failure, if myocardium-only capture is mistakenly accepted as left bundle recruitment, patients would receive harmful right ventricular pacing rather than beneficial resynchronisation.

My aim is to develop an algorithm that can use the lead signals to reliably detect capture and classify the type of capture. I will augment the conventional lead signals with a 2 lead surface ECG from within the generator pocket. This may provide crucial additional information on type of capture.

Figure 2: Comparison of battery saving algorithms with fixed output

1.2 Original Hypothesis

Hypothesis A: A conduction system pacing protocol can be devised for use in any cath lab. **Hypothesis B:** Lead data with a novel sensing vector can detect and categorise conduction system capture, which will allow automated conduction system capture discrimination on implanted devices.

1.3 Rational for Current Study

Currently conductions system pacing is undertaken by experts in tertiary centres with the support of specialised expensive equipment. However, most conventional pacemakers are implanted without this expertise and the advanced equipment. In order to facilitate a wider adoption of conduction system pacing a standardised and simplified implant protocol is required. Our study will devise a simplified, standardised conduction system implantation protocol in order to increase the access to the benefits seen in conduction system pacing.

2. Study Objectives

Primary Objective

The primary objective of this study is to simplify conduction system capture implantation thereby increasing accessibility of the procedure to more operators worldwide.

Secondary Objective

The secondary objectives will be

- 1. To reduce the overall procedure and fluoroscopy time with utilisation of targeted lead deployment.
- 2. Improve conduction system capture discrimination by the device and subsequently increase battery longevity, through development of a unique algorithm.

3. Recruitment

300 patients will be recruited to this study. 100 patients will be recruited to the invasive aspect of this study. These 100 patients will be divided into two-groups: patients 1-50 will be the derivation cohort and will undergo the tests in the derivation arms of Study A and Study B, patients 51-100 will be the validation cohort and will undergo the tests in the validation arms of Study A and Study A.

200 patients with a conduction system device in situ prior to commencement of this study, under pacing follow-up will also be recruited.

Invasive study recruitment

100 prospective patients with an indication for a pacemaker will be recruited from Imperial College Healthcare NHS trust. The direct care team will screen the records and identify patients that are suitable for the study. There will be two groups of patients:

1. Derivation cohort

These patients will undergo the research protocols of the studies. The data will be collated and analysed to develop our unique algorithms. This group will consist of the first fifty patients recruited (patients 1-50).

There will be three groups in this cohort

- 1. Group 1 (all 50 patient): These will undergo
 - a. Preimplant: ECG, echocardiography, ultra-high frequency ECG and MRI
 - b. Intra-implant: Right ventricular mapping, ultra-high frequency ECG and echocardiography
- 2. Group 2 (24 patients): These patients will undergo
 - a. Preimplant: ECG, echocardiography, ultra-high frequency ECG, MRI
 - b. Intra-implant: Right ventricular mapping, ultra-high frequency ECG, echocardiography and ECGi
- 3. Group 3 (15 patients): These patients will undergo
 - a. Preimplant: ECG, echocardiography, ultra-high frequency ECG and MRI
 - b. Intra-implant: Right ventricular mapping, ultra-high frequency ECG echocardiography and arterial access for left ventricular mapping and invasive blood pressure monitoring

2. Validation cohort

The step by step algorithms devised from the data collected from the derivation cohort to improve the conduction system lead implant will be prospectively applied on these patients and the outcomes will be assessed. This group will consist of the second fifty patients recruited (patients 51-100).

Conduction system implant follow-up recruitment

Prospective, pseudonymised electrical data from 200 patients with a chronic conduction system device in situ, that are under follow up will be collected. They will undergo the standard clinical pacing checks and manoeuvres.

The 100 prospectively recruited patients and the 200 patients with a chronic conduction system lead will undergo a consent process. The direct care team will obtain consent to share their information with the research care team. Once the patient has consented to their information being shared, a member of the research team will contact the patient and explain the details of the research study. Written consent will be gained prior to any procedures taking place.

Patients will be consented to take part in the ECGi (Derivation Cohort, Group 2), invasive bloodpressure monitoring and left ventricular mapping (Derivation cohort, Group 3) sub-studies at the time of recruitment, until recruitment target for these sub-studies are met.

Figure 3: A diagram to illustrate patient recruitment for **Study A**. A total of 100 patients will be recruited. Patients 1-50 will be the derivation cohort and 51-100 will be the validation cohort. Within the derivation cohort, some patients will undergo ECGi, additional arterial access and intracardiac echo (ICE), some will undergo two of these additional tests, some will undergo one and some will not undergo any at all. All patients in the derivation cohort will undergo preimplant ECG, echocardiography, ultra-high frequency ECG (UHF ECG) and MRI, as well as right ventricular mapping, UHF ECG and echocardiography during the implant.

Figure 4: Recruitment of patients in Study B

4. Methodology

4.1 Derivation

Study A:

In Study A the derivation cohort will comprise of 50 prospectively recruited patients. These patients will undergo the research protocol. In these patients, we will attempt to implant a permanent conduction system pacing lead, in lieu of the RV or LV lead. The lead will be implanted by operators who have implanted more than 40 leads to overcome the learning curve.

The participants will undergo the following procedural steps after written informed consent is gained:

- Pre-implant Cardiac MRI (Non-invasive) Patients will undergo cardiac MRI as part of their standard clinical care. As it is an MRI there will be no radiation exposure. Gadolinium contrast will be used to better define anatomy and to assess fibrosis.
- 2. Pre-implant 12-lead ECG Patients will undergo a surface 12-lead ECG as part of their standard clinical care.
- 3. Pre-implant echocardiogram Patients will undergo transthoracic echocardiogram as part of their standard clinical care.
- Pre- and intra-procedural UHF-ECG (Non-invasive) UHF-ECG will be recorded with the aim of assessing the level of conduction system block (during intrinsic conduction) and to establish capture type and degree of correction of conduction system disease. This could potentially help in choosing between His-bundle pacing

and left bundle pacing. This is a non-invasive surface ECG, similar to a 12-lead ECG, that is collected over several heart beats.

5. ECGi (Non-invasive activation map)

With pre-procedural CT

A subgroup of patients will undergo non-invasive electrical mapping using a specialised vest with multiple electrodes called ECGi. The ECGi system involves a 252 electrode ECG vest to record activation of the entire heart in a single beat. Patients have a CT scan with the vest on, so the exact anatomical location of the electrodes relative to the heart can be determined. ECGi can provide electrical activation maps and can be used to calculate the left ventricular activation time (LVAT). This is an optional procedure and the patient can participate in the study without the ECGi map.

6. Electro-anatomical 3D mapping (Invasive) As standard, an infraclavicular incision will be made and access to the venous system gained.

a. Right ventricular map

The mapping catheter will be passed into the right ventricle via a sheath through the same venous access site used for the pacemaker leads. Once the anatomical and electrical maps are collected of the right heart, the mapping catheter will be removed and the conduction lead will be placed in the same sheath.

We will then pace from multiple sites during the process of endocardial mapping. The lead will not be deployed at these sites. The lead tip will be in contact with the myocardium. This form of electrical pace mapping is standard clinical practice during pacemaker implantation. I will collect the electrical information from the lead, ECGs and EGMs at these sites in order to identify reliable hallmarks to guide lead deployment at the target site. Through this process I will identify areas of successful and unsuccessful implantation and areas to avoid lead deployment.

The anatomy maps will be correlated with fluoroscopy and cardiac MRI to characterise the appearance of the lead in relation to the the structures of the heart, not only within normal chamber dimensions but also abnormal chamber dimensions.

In the event of difficult lead implantation and lead deployment in unconventional areas, cardiac MRI will be used retrospectively to identify areas of septal fibrosis and variations in anatomy. The electrical hallmarks of fibrosis will be identified using EGM, lead parameters and 12-lead ECG.

b. Left ventricular map

If the patients consent, 15 of the 50 participants will undergo left ventricular electro-anatomical mapping to assess ventricular activation patterns when a left bundle lead is deployed through the septum. The patients will have additional access from the right femoral artery in order to access the aortic circulation. The mapping catheter will be delivered to the left ventricle through a retrograde approach. The left ventricle will be mapped at two points of lead deployment

- 1. Lead in deep septum
- 2. Lead at left bundle

The lead will pace at each of these points of deployment and the activation maps will be collected.

Haemodynamic outcomes of left septal and left bundle pacing, using invasive and noninvasive blood pressure monitoring will be assessed. Invasive blood pressure will be collected from the femoral arterial access already obtained for the mapping catheter, where the sheath will be connected to a pressure inducer. Non-invasive blood pressure will be collected using a high precision beat by beat blood pressure cuff that is placed on the index finger (Finometer). These patients will undergo additional consent in which the risks and benefits of the arterial access and the left ventricular maps will be explained. This is an optional procedure and the patient can participate in the study without undergoing a left ventricular map or invasive blood pressure monitoring.

5. Echocardiogram (Invasive and Non-invasive)

During lead deployment we will visualise lead-septum interaction from echo and fluoroscopic imaging. Echocardiography directly visualises lead orientation, entanglement and progression. Characteristics of successful and unsuccessful deployment, lead progression and lead trajectory will be identified and how this is seen on fluoroscopy. The aim is to use this data to develop the algorithm to inform us whether deployment is progressing well or not well and if so, what is the reason for failure of lead progression.

In a subgroup of patients, we will perform intracardiac echo to visualise the lead, if patients consent to this test. This will involve access from the right femoral vein for these patients. These patients will be additionally consented on implications and benefits of intracardiac echo to the procedure. This is an optional procedure and the patient can participate in the study without undergoing intracardiac echocardiogram.

Those who do not undergo an intracardiac echocardiogram, will have their leads visualised by transthoracic echocardiography (if there are adequate windows) or paediatric transoesophageal echocardiography (TOE), which will eliminate the need for sedation. Participants undergoing TOE will have additional consent.

The right heart mapping will add 10 minutes to the overall procedure time. Left ventricular maps, will add a total of 14 minutes (7 minutes per map). The echocardiography will add 5 minutes to the overall procedure time which will include gaining additional access in ICE, visualisation of the lead and removal.

The aim is that the protocol we will develop will use information which can be acquired from the pacing lead, surface ECG and fluoroscopy without the need for pre-procedure MRI scans, electroanatomical mapping or intra-procedure echocardiography (we will use these systems in our study to help develop and validate the algorithm in addition to understanding and correcting mechanisms of failure).

The ECG, lead parameters (seen on the pacing system analyser (PSA), a machine used to test the pacemaker leads) and fluoroscopic hallmarks of optimal initial deployment positions and optimal lead-septum interactions will be converted to a step-by-step guide for implanters without the need of specialised EP equipment, to achieve conduction system pacing in a systematic and reliable way. The diagnostic characteristics on 12-lead ECG and lead parameters will be analysed by software that can be integrated into the PSA.

Study B:

In patients 1-50 undergoing implantation of conduction system pacemakers, I will collect a 2-lead surface ECG alongside conventional lead data. A surface 12-lead ECG will be collected as well. The patients will undergo the standard pacing manoeuvres for conduction system pacing. The patient will be paced using the PSA and a 12-lead ECG and 2-lead ECG will be collected via Bard, a computer software that is able to collect highly accurate ECG traces of the heart using mapping catheters placed inside the heart and the surface ECG.

I will also collect prospective data from 200 patients with a chronic conduction system lead implant under device follow-up to obtain EGM, 12 -lead ECG and the 2-lead ECG recordings of multiple pacing and sensing configurations. These patients will be attending for routine appointments. The pacing and sensing configurations are undertaken as part of routine checks. The direct care team will identify the patients that are suitable and obtain consent for participating sharing their information with the research team. The research team will contact the patients and obtain informed written consent. During the follow-up appointment, a member of the research team will apply the 2-lead ECG and the direct care team will perform the manoeuvres. The research team will collect data.

I will work with my team to develop algorithms to reduce the impact of local muscle noise. I will improve device diagnosis of conduction system capture using standard lead data, plus the 2-lead ECG. I expect this to be achievable by identifying EGM features that are highly discriminant and organising these into a systematic algorithm with a defined sensitivity and specificity for each capture type.

1.2 Validation

Study A:

A further 50 patients will be prospectively recruited that will make up the validation cohort for Study A. These patients will undergo a conduction system pacemaker as standard clinical practice. We will prospectively apply the step-by-step algorithm derived above to implant the conduction system lead using standard equipment alone; fluoroscopy, PSA and 12-lead ECG. We will assess the success rate, conduction system capture threshold, procedure time and fluoroscopy time. Although all operators will be highly experienced device implanters, these implants will include operators who are new to conduction system lead implantation.

The outcomes will be assessed against patients undergoing conventional methods of conduction system implantation (50 patients) and right ventricular pacing (50 patients).

Study B:

I will run the device algorithm to discriminate capture on patients 51 to 100. Through this I will establish my algorithm's accuracy with the addition of the 2-lead ECG against the gold-standard of combined 12-lead ECG, EGM and pacing manoeuvre diagnoses. These are standard clinical practices. I will test whether inclusion of the pocket EGM contributes to the algorithm's accuracy.

Follow-up

Patients will be followed up 6 weeks after device implantation and again at 1 year. These follow-up appointments will include a wound check at 6 weeks and device interrogation at 6 weeks and 1 year.

Figure 5: A flow diagram demonstrating the investigations the patient will undergo during the course of the Study A

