1.4 Study Outcome Measures

Primary Outcome Measures

A1: Success rates of conduction system lead implant (novel workflow vs conventional methods)

B1: Assess accuracy of conduction system diagnosis by the device with additional information from 2-lead ECG

- A2: Procedure and fluoroscopy times of the streamlined workflow to current conventional methods *of His-bundle and Left-bundle pacing*
- A2: Procedure and fluoroscopy times of the streamlined workflow of conduction system implant to current *right ventricular pacing*
- A2: Assess capture threshold of His-bundle and Left-bundle pacing from the optimised workflow to that of conventional methods of conduction system implantation
- A2: Define left bundle area capture diagnostics and delineate differences between left ventricular septal pacing.
- B2: Improvement in device battery life with novel device algorithm applied

5 Participant Entry

- 5.1 Pre-registration Evaluations
- 5.2 Inclusion Criteria
 - 1. Patients with a ventricular pacing indication: high grade atrioventricular block and symptomatic trifasicular, bifasicular block or left bundle branch block LBBB for cardiac resynchronisation therapy
 - 2. Adults willing to take part (ages 18 100 years old)
 - 3. Able to give consent.

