In **Study A**, I want the validation cohort to be big enough to calculate the success rate percentage with an error margin (standard error) of <10 percentage points in line with primary outcome A1. Similarly, for **Study B**, I want the validation cohort to show the accuracy of my algorithm with an SE under 10 percentage points in line with primary outcome B1. The standard error of a proportion p, in a sample of n patients, is $\sqrt{[p(1-p)/n]}$, i.e. $n=p(1-p)/SE^2$. Applying SE=0.1 (worst-case proportion 0.5) reveals the bare-minimum n required is $0.5*0.5/0.1^2=25$. I will have 50, to ensure the SE <10 percentage points.

Figure 1: A illustration to demonstrate the primary and secondary outcomes of Study A and Study B. * Sample size calculations indicate 50 patients will provide >80% power (see Section 8, statistics and data analysis for more information)

9 Regulatory issues

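### Primary outcome A1 pools all 50 validation implants, with no stated number by operators new to conduction system pacing, so a high A1 cannot by itself show that the procedure is accessible to more operators

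*Protocol*

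**What the plan says.** Protocol, Section 2 (Study Objectives) gives the primary objective as to "simplify conduction system capture implantation thereby increasing accessibility of the procedure to more operators worldwide". Section 1.3 (rationale) explains for whom: "most conventional pacemakers are implanted without this expertise and the advanced equipment". Section 1.1, Challenge A1, describes the present gap: "Experienced centres achieve implant success of 95%, but centres with new conduction system implanters (but highly experienced pacemaker implanters) have rates as low as 56" per cent.

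The primary outcome in 1.4 (Study Outcome Measures) is "A1: Success rates of conduction system lead implant (novel workflow vs conventional methods"). It is a single rate per group, with no split by operator experience.

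On who implants, 4.1 (Derivation, Study A) sets a threshold for the derivation cohort: operators must have implanted more than 40 leads. For the validation cohort, 1.2 (Validation, Study A) says that all operators are highly experienced device implanters and that "these implants will include operators who are new to conduction system lead implantation". It gives neither a number nor a share of implants, and does not define new.

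Section 8 sizes the validation cohort as a whole: "I want the validation cohort to be big enough to calculate the success rate percentage with an error margin (standard error) of <10 percentage points".

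**The concern.** The objective is about operators who do not yet have this expertise, but the primary outcome is an average over them and operators who do. On the protocol's own figures, experienced centres have little left to gain. The success rate of the pooled cohort therefore depends heavily on how many of the 50 implants new operators perform, and the protocol leaves that number open. A few such implants would satisfy 1.2 as written.

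The trial could then report a high A1 and conclude that the workflow opens the procedure to more operators, when the new operators in it did no better than before. The precision stated in Section 8 would also be read as applying to that conclusion, although it describes the pooled rate.

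**Working it through.** **Inputs.** Validation n = 50, p = 0.5 and target SE = 0.1 (Section 8). Success rates of 95% and 56% (Section 1.1); these are centre-level figures, and 56% is the low end. The number m of the 50 implants done by new operators is not given, so a range is shown. A 70% starting rate for new operators is an added assumption, used as a less extreme case.

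**Step 1: the plan's own figure.** n = p(1−p)/SE² = 0.5 × 0.5 / 0.1² = 25, as Section 8 states. At n = 50, SE = √(0.25/50) = 7.1 points. The arithmetic is right and the target is met for the pooled rate.

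**Step 2: pooled rate if the workflow brings no benefit.** Pooled rate = [(50 − m) × 0.95 + m × r] / 50, where r is the new operators' success rate.

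| m | r = 56% | r = 70% |
|---|---|---|
| 5 | (42.75 + 2.8)/50 = 91.1% | (42.75 + 3.5)/50 = 92.5% |
| 10 | (38 + 5.6)/50 = 87.2% | (38 + 7)/50 = 90.0% |
| 25 | (23.75 + 14)/50 = 75.5% | (23.75 + 17.5)/50 = 82.5% |

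With 10 or fewer new-operator implants, the pooled rate stays at 87% or above even though nothing has improved for new operators.

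**Step 3: precision for new operators, by Section 8's formula.** SE = √[p(1−p)/m].

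| m | p = 0.5 | p = 0.95 |
|---|---|---|
| 5 | 22.4 points | 9.7 points |
| 10 | 15.8 points | 6.9 points |
| 20 | 11.2 points | 4.9 points |
| 50 | 7.1 points | 3.1 points |

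At Section 8's own worst case, the margin for new operators is well above 10 points when they do few implants. If nearly all their implants succeed, it is below 10 points even with 5.

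**The case against.** **Section 8 makes no false claim.** It promises its precision for the validation cohort, and 7.1 points keeps that promise. This stands. A reader might infer that the sample size calculation is wrong; it is not. What it lacks is a statement that the figure does not extend to new operators.

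**New operators are not named as the target.** The objective says more operators, and Hypothesis A, that the protocol should be usable in any catheter laboratory, is at least as much about equipment as about skill. Experienced operators working with standard equipment alone do test that part. This stands too: their implants are informative, and the pooled rate has a use. But the rationale also names missing expertise, and the success figures in 1.1 contrast experienced centres with new implanters. The accessibility claim therefore needs the new-operator result.

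**Subgroup reporting belongs in the SAP.** A stratified table could be left there. The number of new-operator implants could not, because it is settled as the implants are done and no later analysis plan can supply it.

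**A1 is a comparison, so a high rate would not be read alone.** With the same operator mix in both groups, a useless workflow would show no difference on average. But 1.2 does not describe the operators in the conventional group, and Section 8 sizes A1 as a single rate. Even with equal mixes, a real gain among new operators is scaled down by their share: with 10 of 50, a rise from 56% to 95% moves the pooled rate by only 10/50 × 39 = 7.8 points.

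**Conclusion.** The point holds as a gap between the primary objective and the outcome meant to support it. A high pooled A1 cannot by itself support a conclusion about accessibility, because with no workflow benefit it would still be about 91%, 87% or 76% with 5, 10 or 25 new-operator implants. These sizes assume that the protocol's centre-level rates apply to individual operators. If new operators start at 70%, the pooled rate with 10 such implants is 90%, so the masking is then greater.

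Three stronger readings go beyond the document:

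- A reader might infer that A1 could come from experienced operators alone. The protocol says new operators will take part; only their number is open.
- A reader might infer that at least 26 of the 50 implants must be by new operators for the SE to fall below 10 points. That is so only at p = 0.5. At p = 0.56, 25 suffice (9.9 points), and at p = 0.95, 5 do (9.7 points). Such a minimum would also constrain who operates on patients, and the protocol's figures do not justify that.
- A reader might link this to the footnote claiming more than 80% power. Section 8 specifies no test, and any power figure by operator mix depends on the assumed starting rate. The footnote is a separate question.

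**What to change.** **In 1.2 (Validation) and 1.4:**
- State that A1 is reported separately for implants by new and by experienced operators.
- Record the first operator's number of prior conduction system implants for each case.
- Define new, for example against the 40-lead threshold that the protocol already uses for the derivation cohort.
- State that the accessibility conclusion rests on the new-operator rate with its 95% interval. The pooled rate is then supportive, and informs the standard-equipment part of Hypothesis A.

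**In Section 8:**
- State that the SE of under 10 percentage points refers to the pooled rate.
- Give the expected number of new-operator implants and the precision that number provides.

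**Cost:** protocol wording, one extra recorded field per implant and one stratified table. The price is a wider stated margin for the group that matters most. No additional patients are needed, and the allocation of cases to operators need not change.
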